Official title of project: INvestigating Fear Of Recurrence as a modifiable Mechanism of behavior change to improve medication adherence in acute coronary syndrome patients (the INFORM Study)

NCT number of project: NCT03853213

Document date: 06/21/2019

Principal Investigator: [name]

1. Study Purpose and Rationale

Acute coronary syndrome (ACS; myocardial infarction or unstable angina) is a leading cause of morbidity and mortality in the U.S., and survivors are at high risk for recurrent cardiovascular disease (CVD) events, particularly if they do not adhere to risk-reducing medications. Failure to take aspirin as prescribed is associated with 75% increased risk of recurrent CVD events or mortality,¹ and half of ACS patients are nonadherent to secondary risk medications by 1 year after the index ACS event. Emerging evidence suggests that posttraumatic stress disorder (PTSD) symptoms following ACS and other cardiovascular disease (CVD) are strongly associated with medication nonadherence, and ~50% of patients report symptoms.²⁻⁴ Indeed, our pilot data suggest that those who are most distressed by a CVD event (as evidenced by PTSD symptoms) are also those least likely to behave in ways that would reduce the probability of CVD event recurrence.⁵

PTSD caused by a life-threatening medical event is reliably associated with heightened fear of CVD event recurrence.⁶⁻⁸ We and others have proposed that ACS-induced PTSD symptoms may be distinct from PTSD due to stereotypical traumatic events such as combat or assault, because intrusive thoughts may be focused on fear of CVD event recurrence (FoR) in the future, rather than preoccupation with the past cardiac event.⁹ Ironically, rather than promoting preventive health behaviors, FoR may be associated with worse medication adherence, as patients who develop PTSD symptoms report avoiding medications because they do not want to be reminded of their CVD risk.¹⁰ It is possible that the small/distal perceived CVD benefit of adherence relative to the large/proximal psychological benefit of avoidance¹⁰ may result in nonadherence. We now propose to determine whether FoR is a modifiable mechanism linking PTSD symptoms with nonadherence to aspirin for secondary prevention in ACS patients.

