We will test this mediational hypothesis using conditional process modeling with the PROCESS macro in SPSS.²¹ Although we will likely have insufficient power to test the question definitively, the results will inform whether a future larger trial is warranted. The behavioral outcome in the model is heart medication adherence from the eCAP data: mean proportion of adherent days in the 2-month monitoring period that occurs within several months after hospital discharge. The predictor is group (intervention, control). The mediator is pre-to-post change in FoR from Time 1 to 2. For a secondary analysis, we will test the outcome as the magnitude of the slope of change in weekly proportion of adherent days during the 2 months. We will evaluate whether there is a significant indirect effect that supports the notion that the intervention vs. the control training engaged the target mechanism in such a way that changes in the target predicted improved heart medication adherence over the month-long intervention.

Exploratory Aim 1.

We will test for off-target intervention effects on future time perspective, as well as the alternative mediation path through improvement in future time perspective.

The test will be structured as for Specific Aim 3 but with pre-to-post change in future time perspective as the tested mediator.

Exploratory Aim 2.

We will test whether the intervention is associated with greater increases in physical activity relative to the control group and whether this association is mediated by changes in FoR or future time perspective.

The test will be structured as for Specific Aim 3 and Exploratory Aim 1 but with physical activity as the tested behavioral outcome measure instead of medication adherence.

Power analysis.

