In prior research with $N = 97$ at Time 1 using a similar intervention in cancer patients, a moderate effect size (Hedges $g = 0.54$) was found for differences in FoR between the intervention ($n = 64$) and control ($n = 36$) groups after 3 months and a somewhat smaller effect size (Hedge's $g = 0.35$) immediately after the 1-month intervention.¹³ Using G*Power 3.1,²² we tested a range of effect sizes for two levels of power. We determined that the present study is conservatively powered to change FoR in a fixed-effects one-way ANOVA with an effect size f of 0.35 or larger with a sample size of $N = 100$ (50 intervention, 50 control), given alpha = .05 and an intention-to-treat design in which missing data due to attrition are handled with multiple imputation.

4. Study Procedures

Patients will be considered for enrollment in the present study who are currently enrolled in AAAR7350 (the PHS study), who signed consent for AAAR7350 within the last 6 weeks (i.e., 42 days), who have indicated they are willing to hear about other research studies, and who have an Elevated Threat Perception score. Consent will be obtained using an IRB-approved consent form.

Pre-training/Time 1: For patients consenting to the study in the hospital, the pre-training session ideally occurs at this same visit. The RA will assess the potential mechanisms of behavior change verbally. At the end of this session, each patient will be given a tablet and an eCAP bottle with a brief explanation of their use. The estimated duration of this session is 45 minutes, including the consent process, questionnaires, and the brief training in the use of the tablet. A subset of patients will complete the consent process and receive the devices (eCAP bottle, tablet) with a brief training in the hospital and will then separately complete the questionnaires verbally by phone within several days. A separate subset of patients will complete the Time-1 session at CUMC sometime after hospital discharge but before 6 weeks (i.e., 42 days) have elapsed from the time of consent to the protocol AAAR7350.

Training phase: Random group assignment to the intervention or control group will be determined in a double-blind way by the programmed tasks on the tablet for each participant.

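### In the Aim 3 mediation model about half of the adherence days fall before the mediator is fully measured, so the 8-week indirect effect cannot by itself show that change in fear of recurrence came before adherence

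*Combined protocol and SAP*

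**What the plan says.** Statistical Procedures, Specific Aim 3, sets out a mediation model with group as predictor. "The mediator is pre-to-post change in FoR from Time 1 to 2". The outcome is the "mean proportion of adherent days in the 2-month monitoring period that occurs within several months after hospital discharge". The plan then adds a second outcome: "we will test the outcome as the magnitude of the slope of change in weekly proportion of adherent days during the 2 months". The paragraph ends by asking whether "changes in the target predicted improved heart medication adherence over the month-long intervention". The only limitation it admits is power: "Although we will likely have insufficient power to test the question definitively".

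Exploratory Aim 1 takes over the design: "The test will be structured as for Specific Aim 3 but with pre-to-post change in future time perspective as the tested mediator".

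The timing is in Study Design and Study Procedures. The eCAP bottle is handed over at about Time 1 or mailed, is in use during the training weeks, and goes back 8 weeks after Time 1. Time 2 is a telephone interview a few days after the 4-week training ends.

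**The concern.** The model is meant to support a statement that change in the target predicted adherence, and its result is to inform whether a larger trial is justified. That statement needs the mediator to be settled before the outcome it predicts. Here the mediator is known only at Time 2, while the outcome has been accumulating since about Time 1. An association between them could mean that falling fear improved adherence, that early pill-taking changed fear, or that something else drove both.

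Neither planned outcome starts after Time 2, and neither adjusts for adherence before Time 2. The power caveat does not cover this. Low power concerns precision, whereas this ambiguity would remain in a larger sample.

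The closing sentence adds a second problem. It places adherence in the month of training, whereas the outcome defined in the same paragraph covers two months.

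**Working it through.** **Plan's own figure.** None is given for mediation. The power statement concerns Aim 2: N = 100, f = 0.35, alpha .05, power level not stated. With noncentrality N·f² = 100 × 0.35² = 12.25 on F(1, 98), power is 93.4%. For two equal groups f = d/2, so this is d = 0.70. The g = 0.35 that the plan quotes from the cancer study immediately after training is f = 0.175, with noncentrality 3.06 and power 41%. Both values are used below for the effect of group on FoR.

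**Timing.** Inputs from Study Design and Study Procedures: training ends on day 28, and monitoring runs from about day 0 to day 56. The delays used are assumptions.

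Share of outcome days before Time 2 = (Time 2 day − start day) / (56 − start day).
- Time 2 on day 28: 28/56 = 50%.
- Time 2 on day 31 or 35: 31/56 = 55.4%; 35/56 = 62.5%.
- Bottle mailed and started 7 days late, Time 2 on day 28 or 35: 21/49 = 43%; 28/49 = 57%.

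Days left after Time 2: 56 − 35 = 21 to 56 − 28 = 28.

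**Slope.** The least-squares weight for week w of 8 is (w − 4.5)/42. Absolute weights for weeks 1-4 sum to (3.5 + 2.5 + 1.5 + 0.5)/42 = 8/42, out of 16/42 in all, which is 50%. The slope removes a constant difference in level between patients, but half of its weight still lies in weeks 1-4.

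**Illustration.** The following rests on assumptions that are not in the documents. E and L are standardised adherence before and after Time 2, M is FoR reduction, n = 50 + 50, and d = 0.35. FoR has no effect on adherence. The E-M correlation r has size .2-.3, and the E-L correlation c is .3-.7.
- Reverse path: M = rE + √(1−r²)e + d·group; L = cE + √(1−c²)e.
- Common cause: a stable trait t, with E and L each = √c·t + √(1−c)e, and M linked to E only through t (r positive).

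The mean is (E + L)/2 and the slope is L − E. The lagged model regresses L on M, group and E. False support means that group-to-M and M-to-outcome are both p < .05 in the hypothesised direction.

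| Assumed truth | 8-week mean | Slope | Lagged, adjusted | Mean and slope both |
|---|---|---|---|---|
| Early adherence lowers FoR | 14-33% | at most 0.2% | about 1% | at most 0.1% |
| Early adherence raises FoR | about 0% (14-33% significant in the wrong direction) | 5-18% | about 1% | 0% |
| Stable common cause | 23-40% | about 1% | 5-26% | about 1% or less |

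At d = 0.70 the first entry becomes 32-75%, so the rates depend heavily on the effect size chosen.

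If FoR truly affects adherence (standardised effect .3), the M-to-outcome path is detected as follows, for mean, slope and lagged model in turn:
- effect in weeks 5-8: 35-46%, 72-98%, 88-99%;
- effect in weeks 1-4 only: 68-80%, about 0%, 2-3%.

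For the effect in weeks 5-8, joint power of the lagged model (both paths) is 36-40% at d = 0.35 and 83-93% at d = 0.70.

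**Text conflict.** "mean proportion of adherent days in the 2-month monitoring period that occurs within several months after hospital discharge" covers two months. "changes in the target predicted improved heart medication adherence over the month-long intervention" covers one month, which would end before Time 2.

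**The case against.** The strongest reply is that the plan already contains its own check. In the illustration at d = 0.35, requiring the 8-week mean and the slope to agree holds false support to about 1% or less, about as low as any rule using the added model. This stands, with two limits: the plan states no such rule, and agreement of that pair has less power for an effect in weeks 5-8 (M-to-outcome in both: 33-36%, against 70-98% for slope and lagged model together).

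Several stronger readings are tempting, and the documents do not support them.
- A reader might infer that half of the outcome comes before the mediator. The mediator is a change, and weeks 1-4 run alongside it. Those days precede only its final measurement.
- A reader might infer that the plan is biased towards finding mediation. The sign is unknown. The rationale says that "patients who develop PTSD symptoms report avoiding medications because they do not want to be reminded of their CVD risk". If taking the pill is itself a reminder that raises fear, the 8-week mean is biased against the hypothesis.
- A reader might infer that time order cannot be shown from this trial at all. The limit lies in the planned models; the openings are dated.
- Some patients "receive the devices (eCAP bottle, tablet) with a brief training in the hospital and will then separately complete the questionnaires verbally by phone", so a reader might infer that days before Time 1 are counted and push the share to two thirds. The plan does not say that such days count.
- A reader might want the lagged model to decide the matter. It adjusts away an effect acting during training, when the intervention is delivered, and it stays open to common causes.

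It is also fair that mediation is a secondary part of Aim 3 and is described as likely underpowered. That lowers the stakes but does not remove the ambiguity.

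**Conclusion.** The point holds, at minor to moderate severity. It rests on the timing alone: about half of the outcome days (50-62.5% with monitoring from Time 1; 43-57% if the bottle starts a week late) precede the final measurement of the mediator, and no planned outcome separates the periods. The 8-week indirect effect is therefore an association whose time order that model does not establish. Exploratory Aim 1 shares the limit. Exploratory Aim 2 also borrows the structure, but the timing of its physical activity measure is not given, so it was not assessed.

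The simulated rates show what could happen under assumed correlations, with adherence treated as normal and d set at 0.35 or 0.70. They do not estimate the bias in this trial. A reader might infer that the randomised adherence comparison or Aim 2 is compromised; neither uses the mediator-to-adherence path, so both are unaffected. The mismatch between one month and two months is a plain inconsistency whatever view is taken of the model.

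**What to change.** Keep the 8-week mean and the slope as planned, and state that the slope is analysed with its sign. Pre-specify one added sensitivity model for Aim 3 and Exploratory Aim 1:
- outcome: proportion of adherent days from the day after the participant's Time 2 interview to week 8;
- predictor: group;
- mediator: change from Time 1 to Time 2;
- covariate: proportion of adherent days from the start of monitoring to Time 2.

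Report the 8-week mean, slope and lagged results side by side, with no single model acting as a gate. Describe the 8-week indirect effect as an association whose time order is not established by that model alone. State the limits of the lagged model: 21-28 outcome days instead of 56, little power for effects confined to weeks 1-4, exposure to unmeasured common causes, and a group coefficient that is not a randomised comparison because it conditions on adherence after randomisation. Reconcile the closing reference to a one-month window with the 2-month outcome.

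The cost is a few sentences in the SAP and one extra model per aim. No new data are needed, because the eCAP already records the date and time of each opening (Measures, Medication adherence).

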We will use the Science of Behavior Change (SOBC) experimental medicine approach to identify, measure, and influence FoR and related cognitive mechanisms (e.g., diminished future time perspective), and determine whether change in FoR is related to change in medication adherence. We will enroll N = 100 patients within 6 weeks of first presenting to the emergency department with suspected acute coronary syndrome who reported elevated early symptoms indicative of risk of developing PTSD (threat perceptions) at the time of their emergency department visit.¹¹ In all participants, we will measure FoR using the Concerns About Recurrence Scale (which we have adapted for ACS).¹³ We will also measure future time perspective using an assay from the SOBC measures repository: the Future Time Perspective Scale,¹⁴ to test their association with FoR and nonadherence. Prior to discharge, we will randomize patients to receive a computerized cognitive-affective FoR intervention [8 sessions (30 min/session; 2/week for 4 weeks)¹³ or control task, to test whether the intervention reduces FoR. The brief intervention has successfully reduced FoR in cancer patients. It trains patients to attend away from threatening disease-related cues (e.g., looking away from the word recurrence and instead toward a neutral word such as categories) and to make benign interpretations of ambiguous, potentially disease-related information (e.g., fatigue reflects lack of sleep, not ACS recurrence). Finally, we will test whether the intervention (and/or improvement in FoR) is associated with greater electronically-measured adherence to aspirin or other heart medications, including non-aspirin antiplatelet, beta-blockers, or statins, in the 2 months after discharge.

Specific Aim 1: To measure FoR in ACS patients, and test its associations with ACS-induced PTSD, diminished future time perspective, nonadherence to medications, and lack of physical activity.

Specific Aim 2: To test whether a cognitive-affective intervention reduces FoR in ACS patients.

Specific Aim 3: To test whether patients randomized to the intervention are more adherent to aspirin in the 2 months after discharge for ACS, and secondarily, whether any intervention effect is explained by reduced FoR.

Exploratory Aim 1: We will test for off-target intervention effects on future time perspective, as well as the alternative mediation path through improvement in future time perspective.

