To measure FoR in ACS patients, and test its associations with ACS-induced PTSD, diminished future time perspective, and nonadherence to medications.

We will test the extent to which the hypothesized measures of the behavior change mechanisms in question (FoR, future time perspective) are intercorrelated in ACS patients with elevated acute stress symptoms. First, to test convergent validity, we will assess zero-order correlations among these measures. Specifically, we predict that—across both groups at Time 1 before the intervention—higher FoR will be associated with lower future time perspective (i.e., lower FTPS). Second, we will test whether higher FoR is associated with higher threat perception symptoms and overall lower proportion of days adherent to aspirin. Third, due to the within-subjects design, we will also assess test-retest reliability from Time 1 to 2, both across and within groups. In this way we will ensure that we have valid and reliable measures of our proposed mechanisms of behavior change.

Specific Aim 2.

To test whether a cognitive-affective intervention reduces FoR in ACS patients.

We will conduct a univariate ANOVA to assess the effect of the four-week intervention on pre-to-post change in FoR, the proposed target mechanism. Prior intervention research in cancer patients showed a small to moderate effect size of a cognitive-affective intervention on FoR symptoms (Hedge's g for difference in health worries from pre- to post-intervention = 0.35). In separate unadjusted tests with pre-to-post change in FoR (and in an exploratory test of future time perspective) as the outcome, we will enter group (intervention, control) as the predictor. We will repeat the tests adjusting for factors that may explain variance in health behavior, including demographic information (age, sex, race, ethnicity), medical severity assessed by GRACE risk score¹⁸ and Charlson comorbidity index,¹⁹ and depressive symptoms assessed by PHQ-8 score.²⁰

Specific Aim 3.

To test whether patients randomized to the intervention are more adherent to aspirin in the 2-month monitoring period within the first several months after their suspected ACS event, and secondarily, whether any intervention effect is explained by reduced FoR.

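### The Aim 3 mediation model omits Time 1 fear of recurrence, so its path from FoR change to adherence is generally biased unless adherence depends on change alone

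*Combined protocol and SAP*

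**What the plan says.** Section 3, Specific Aim 3, builds the mediation model from three variables. The predictor is randomised group. For the mediator the plan states: "The mediator is pre-to-post change in FoR from Time 1 to 2". The outcome is the "mean proportion of adherent days in the 2-month monitoring period that occurs within several months after hospital discharge". No covariate is listed. The plan concedes that power is probably insufficient, but says "the results will inform whether a future larger trial is warranted".

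The only covariate list is under Specific Aim 2: "We will repeat the tests adjusting for factors that may explain variance in health behavior". It covers demographics, GRACE, Charlson and PHQ-8. Time 1 FoR is not on it, and the list is not carried over to Aim 3.

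The exploratory aims inherit the specification. Exploratory Aim 1 reads: "The test will be structured as for Specific Aim 3 but with pre-to-post change in future time perspective as the tested mediator". Exploratory Aim 2 follows the same structure with physical activity as the outcome.

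On the mechanism, the documents point two ways. Section 1 sets out to "determine whether change in FoR is related to change in medication adherence", which is a statement about change. Specific Aim 1 is about level: "we will test whether higher FoR is associated with higher threat perception symptoms and overall lower proportion of days adherent to aspirin".

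**The concern.** Randomisation protects the effect of group on FoR change and the total effect of group on adherence. It does not protect the path from FoR change to adherence, because patients are not randomised to their change in FoR. Patients who start with high FoR tend to show larger falls. If baseline FoR is itself related to adherence, given Time 2 FoR, a model containing only the change score mixes that relation into the mediator coefficient.

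The mechanism conclusion rests on a significant indirect effect, which is the product of the group-to-FoR and FoR-to-adherence paths. If adherence follows FoR level, the planned model can shrink or cancel a true indirect effect, and the mechanism may be wrongly discounted when a larger trial is considered. If only baseline FoR matters, the model produces a path of the wrong sign. That would look like an anomaly or a lack of support, not like confirmed mediation.

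**Working it through.** **Plan's own figure.** None is given for the mediation model. The sample size (N = 100, effect size f = 0.35) refers to the Aim 2 ANOVA, and no power is stated with it. Exact power for that test is 93.4%, but nothing below depends on it.

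**Inputs from the documents.** N = 100, 50 per group; a standardised group effect on FoR of 0.35 immediately after the intervention (Power analysis); FoR measured at both times (Section 2).

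**Assumed inputs.** The SD ratio, the Time 1 to Time 2 correlation, the slopes on adherence, the reliability of FoR and a residual SD of 1 are not in the documents.

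**Closed form.** Let M1 and M2 be FoR at Time 1 and Time 2, D = M2 - M1, k = SD2/SD1 and ρ their within-group correlation. Suppose adherence = c·M1 + b·M2, plus a group term and error. Rewriting,

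c·M1 + b·M2 = b·D + (b + c)·M1.

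Leaving out M1, the coefficient on D converges to

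b + (b + c)(ρk - 1)/(1 + k² - 2ρk).

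It equals b only if c = -b (change alone matters) or ρk = 1 (Time 1 FoR is uncorrelated with change). With M1 in the model it equals b.

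**Equal SDs (k = 1).** The fraction is (ρ - 1)/(2 - 2ρ) = -1/2, so the unadjusted coefficient is (b - c)/2 for any ρ:

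- Time 2 only (b = -0.30, c = 0): -0.30/2 = -0.15. Indirect effect: -0.35 × -0.15 = 0.053, against -0.35 × -0.30 = 0.105.
- Both times equally (b = c = -0.15): 0, against -0.15.
- Baseline only (b = 0, c = -0.30): +0.15, against 0.
- Change alone (b = -0.30, c = +0.30): -0.30, no bias.

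**Unequal SDs, Time 2 only.** Share of b retained without adjustment:

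| k | ρ = 0.4 | ρ = 0.6 | ρ = 0.8 |
|---|---|---|---|
| 0.8 | 0.32 | 0.24 | 0.00 |
| 1 | 0.50 | 0.50 | 0.50 |
| 1.25 | 0.68 | 0.76 | 1.00 |

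For example, at k = 0.8 and ρ = 0.4: 1 + (0.32 - 1)/(1 + 0.64 - 0.64) = 0.32.

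**Simulation.** N = 100, 10,000 trials, equal SDs, error-free FoR, group effect -0.35 SD. The indirect effect is counted as detected when both paths have p < .05. Results are for ρ = 0.4 / 0.6:

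| Adherence depends on | Unadjusted | Adjusted for Time 1 FoR |
|---|---|---|
| Time 2 only | 13.1% / 12.8% | 36.5% / 38.8% |
| Both equally | 1.7% / 2.6% | 12.5% / 13.1% |
| Baseline only (no mediation) | 12.9% / 12.7%, virtually all wrong-signed | 2.5% / 3.0% |
| Change alone | 31.8% / 38.0% | 37.3% / 39.0% |

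In the baseline-only case the FoR-to-adherence path taken alone is falsely significant in 37.1% / 25.7% of trials unadjusted, against 5.2% / 5.2% adjusted.

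**Measurement error.** With reliability 0.8 and true-score ρ of 0.7, adjustment helps but does not remove the bias. Time 2 only (truth -0.30): -0.08 unadjusted and -0.21 adjusted, with joint significance 5% and 23%. Baseline only (truth 0): +0.08 and -0.05. The adjusted residual is smaller but lies in the hypothesised direction.

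**The case against.** The strongest reply is that the plan frames the mechanism as change, in Section 1 and again in Aim 3, and under a pure change mechanism the planned coefficient is unbiased. Aim 3 also has a secondary outcome, the slope of weekly adherence, for which a change mediator is a more natural choice. The Aim 1 statement about level is an association test within measure validation, not a causal model. This stands as far as it goes: the documents do not settle which case holds. But a pure change mechanism requires that, at the same Time 2 fear, higher baseline fear goes with better adherence, and the plan gives no reason to expect that. Even in that case, adjustment leaves the estimate unbiased and loses no power in the simulation.

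Other limits also stand. The analysis is secondary and admittedly underpowered, and with true mediation the adjusted model reaches joint significance in only about 12-39% of trials, so a null result is likely either way. Nearly all inputs to the size are assumed, and the share retained runs from 0 to 1, so the documents support a concern but not one number. The plan is silent on a baseline covariate and does not exclude one. Finally, adherence is recorded for about 8 weeks from Time 1 and Time 2 falls at about 4 weeks, so roughly half the outcome precedes the completed mediator. Adding Time 1 FoR does not repair that ordering, nor other mediator-outcome confounding.

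**Conclusion.** The concern holds. As written, the Aim 3 model can halve, cancel or reverse the FoR-to-adherence path, and it is free of this bias only if adherence depends on change alone or Time 1 FoR happens to be uncorrelated with change. The direction and form of the bias follow from algebra. Its size rests on the assumed SDs, correlation, slopes and reliability. "Biased" here is relative to the effect of Time 2 FoR on adherence at a given Time 1 FoR, which is what a mediation reading needs. The effects of group on FoR change and on adherence are not touched. The change should be made: the mechanism result is meant to inform a larger trial, and an analysis already short of power should not carry an avoidable bias as well.

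**What to change.** Enter Time 1 FoR as a covariate in both the mediator and the outcome equation of the Aim 3 model. In Exploratory Aims 1 and 2, enter the Time 1 value of whichever mediator is tested, FoR or future time perspective, in both equations. State that measurement error in the mediator can leave some residual bias after adjustment.

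The cost is one or two sentences in the analysis plan and one degree of freedom per covariate. Both measures are already collected at Time 1.
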